1.2 Demographics and Other Baseline Characteristics	13
1.2.1 Summary of Demographics and Other Baseline Characteristics	13
1.2.2 Medical History and Concurrent Medical Conditions	15
1.2.3 Medication History and Concomitant Medications	16
1.3 Treatment Compliance.....	16
1.3.1 Study Drug Exposure and Compliance.....	16
2 Efficacy Analysis.....	17
2.1 Primary Endpoint(s) and Analytical Methods.....	17
2.1.1 Primary Analysis.....	17
2.1.2 Secondary Analysis (1).....	18
2.1.3 Secondary Analysis (2).....	18
2.2 Secondary Endpoint(s) and Analytical Methods.....	19
2.3 Other Analysis/Additional Endpoint(s) and Analytical Methods	22
2.4 Statistical/Analytical Issues	31
2.4.1 Adjustments for Covariates.....	31
2.4.2 Handling of Dropouts or Missing Data.....	31
2.4.3 Interim Analyses and Data Monitoring.....	31
2.4.4 Multicenter Studies	31
2.4.5 Multiple Comparison/Multiplicity	31
2.4.6 Use of an “Efficacy Subset” of Subjects.....	32
2.4.7 Active-Control Studies Intended to Show Equivalence or Non-Inferiority	32
2.4.8 Examination of Subgroups.....	32
3 Safety Analysis	33
3.1 Treatment-Emergent Adverse Event.....	33
3.1.1 Overview of Treatment-Emergent Adverse Events	33

3.1.2 Displays of Treatment-Emergent Adverse Events.....	34
3.2 Pretreatment Events and Placebo Lead-in Adverse Events	35
3.2.1 Displays of Pretreatment Events.....	35
3.2.2 Displays of Placebo Lead-in Adverse Events	36
3.3 Laboratory and Other Safety Data	37
3.3.1 Laboratory Test Results	37
3.3.2 Vital Signs, Physical Findings and Other Observations Related to Safety.....	38
4 Significance Level and Confidence Coefficient	44
Amendment History (Version Management).....	45
[Appendix 1] Change Comparison Table for Lu AA21004/CCT-004	1
[Appendix 2]Definition of PCS Criteria	1

Glossary

- Treatment-emergent adverse event (TEAE): An adverse event which occurs on or after the start of double-blind study drug
- Placebo lead-in adverse event: An adverse event which occurs on or after the start of placebo lead-in study drug before the start of double-blind study drug
- Drug-related adverse event: An adverse event that is considered to be either probable, or possible related to the double-blind study drug will be treated as related.
- Descriptive statistics: number of subjects, mean, standard deviation, maximum, minimum, and quartiles
- PCS: Potentially Clinically Significant
- Study Day: The day before the first dose of the double-blind study drug will be defined as Study Day -1 and the day of the first dose will be defined as Study Day 1.
- Follow-up Day: The day after the last dose of the double-blind study drug will be defined as Follow-up Day 1.
- Treatment Groups: Placebo, Lu AA21004 10 mg, Lu AA21004 20 mg
- MADRS total score: Sum of the 10 MADRS items
- HAM-D17 total score: Sum of the 17 HAM-D items
- HAM-D21 total score: Sum of the 21 HAM-D items
- SDS total score: Sum of the 3 SDS items
- MADRS response: Percentage of subjects whose MADRS total score decreased by a greater than or equal to 50% from baseline
- MADRS remission: Percentage of subjects whose MADRS total score decreased to 10 or less

Definition of TIME WINDOW

For each test/observation/evaluation item, all evaluable data (non-missing and acceptable according to the “Handling Rules for Analysis Data”) will be handled according to the following rules.

For each visit other than Week 8 (LOCF), observation in the corresponding time interval will be used. If more than one observation lies within the same visit window, the observation with the closest Study Day to the scheduled Study Day will be used. If there are two observations equidistant to the scheduled Study Day, the later observation will be used. The difference from the scheduled Study Day will be judged based on the Study Day and Follow-up Day.

For Week 8 (LOCF), the last observation obtained in the corresponding time interval will be used.

MADRS, CGI-S

Visit	Scheduled Study Day (days)	Time Interval (days)	
		Study Day	Follow-up Day
Screening	Study Day: -22	<= -12	-
Placebo lead-in	Study Day: -8	-11 - -5	-
Baseline (Week 0)	Study Day: -1	-4 - 1	-
Week 1	Study Day: 7	2 - 10	<8
Week 2	Study Day: 14	11 - 21	<8
Week 4	Study Day: 28	22 - 35	<8
Week 6	Study Day: 42	36 - 49	<8
Week 8	Study Day: 56	50 <=	<8
Week 8 (LOCF)	-	2 <=	<8

HAM-D

Visit	Scheduled Study Day (days)	Time Interval (days)	
		Study Day	Follow-up Day
Screening	Study Day: -22	<= -12	-
Placebo lead-in	Study Day: -8	-11 - -5	-
Baseline (Week 0)	Study Day: -1	-4 - 1	-
Week 8	Study Day: 56	2 <=	<8
Week 8 (LOCF)	-	2 <=	<8

CGI-I

Visit	Scheduled Study Day (days)	Time Interval (days)	
		Study Day	Follow-up Day
Baseline (Week 0)	Study Day: -1	<= 1	-
Week 1	Study Day: 7	2 - 10	<8
Week 2	Study Day: 14	11 - 21	<8
Week 4	Study Day: 28	22 - 35	<8
Week 6	Study Day: 42	36 - 49	<8
Week 8	Study Day: 56	50 <=	<8
Week 8 (LOCF)	-	2 <=	<8

SDS

Visit	Scheduled Study Day (days)	Time Interval (days)	
		Study Day	Follow-up Day
Placebo lead-in	Study Day: -8	≤ -5	-
Baseline (Week 0)	Study Day: -1	-4 - 1	-
Week 8	Study Day: 56	$2 \leq$	< 8
Week 8 (LOCF)	-	$2 \leq$	< 8

DSST, PDQ-5

Visit	Scheduled Study Day (days)	Time Interval (days)	
		Study Day	Follow-up Day
Placebo lead-in	Study Day: -8	≤ -5	-
Baseline (Week 0)	Study Day: -1	-4 - 1	-
Week 1	Study Day: 7	2 - 10	< 8
Week 8	Study Day: 56	$11 \leq$	< 8
Week 8 (LOCF)	-	$2 \leq$	< 8

Laboratory Value, Weight, ECG

Visit	Scheduled Study Day (days)	Time Interval (days)	
		Study Day	Follow-up Day
Screening	Study Day: -22	≤ -12	-
Placebo lead-in	Study Day: -8	-11 - -5	-
Baseline (Week 0)	Study Day: -1	-4 - 1	-
Week 4	Study Day: 28	2 - 42	< 8
Week 8	Study Day: 56	$43 \leq$	< 8

Vital Sign, C-SSRS

Visit	Scheduled Study Day (days)	Time Interval (days)	
		Study Day	Follow-up Day
Screening	Study Day: -22	<= -12	-
Placebo lead-in	Study Day: -8	-11 - -5	-
Baseline (Week 0)	Study Day: -1	-4 - 1	-
Week 1	Study Day: 7	2 - 10	<8
Week 2	Study Day: 14	11 - 21	<8
Week 4	Study Day: 28	22 - 35	<8
Week 6	Study Day: 42	36 - 49	<8
Week 8	Study Day: 56	50 <=	<8

Others

- Duration of exposure to double-blind study drug (days): date of last dose of double-blind study drug – date of first dose of double-blind study drug + 1
- Double-blind study drug compliance (%): number of double-blind study drugs taken / duration of exposure to double-blind study drug × 100 (rounded off to one decimal place)
- $QT_{CF} \text{ interval} = (QT \text{ interval}) / ([QT_{CB} \text{ interval}]^2 / [QT \text{ interval}]^2)^{0.33}$ (rounded off to the whole number)
- Among the laboratory test items, the following data will not be included if it is from a postprandial specimen.
Glucose, lipids (triglycerides, total cholesterol, HDL cholesterol, LDL cholesterol [Direct method])
-

1 Study Subjects, Demographic, and Other Baseline Characteristics

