2.1 Primary Endpoint(s) and Analytical Methods

2.1.1 Primary Analysis

Analysis Set: Full Analysis Set

Analysis Variable(s): Change from baseline in the MADRS total score at Week 8 of treatment with double-blind study drug

Analytical Method(s): Primary efficacy analysis will be performed based on a mixed model for repeated measurements (MMRM) analysis of covariance with change from baseline in MADRS total score at each post-dose visit as a dependent variable, and visit, treatment group, visit-by-treatment group interaction, baseline MADRS total score-by-visit interaction as fixed effects.

Comparisons between each Lu AA21004 group and the Placebo group will be performed at Week 8 of treatment with double-blind study drug. For the adjustment of freedom degree, Satterthwaite method will be used. For covariance structure analysis among the subjects, the same, unstructured covariance matrix is assumed.

[Model]

Change from baseline in the MADRS total score = Visit + Treatment group + Treatment group \times Visit + baseline MADRS total score \times Visit

Holm adjustment will be used for multiplicity for the comparison. That is,

$$H_{01}: \mu_{\text{Placebo}} = \mu_{10 \text{ mg}}$$

$$H_{02}: \mu_{\text{Placebo}} = \mu_{20 \text{ mg}}$$

A p-value for each null hypothesis will be set to be P_1 and P_2 . A test will be performed according to the following procedures after setting P_1 and P_2 in an ascending order as $P^{(1)}$ and $P^{(2)}$ and setting the corresponding null hypotheses as $H^{(1)}$ and $H^{(2)}$.

Step 1: In the case of $P^{(1)} > 0.025$, end the test procedures by holding null hypotheses $H^{(1)}$ and $H^{(2)}$. In the case of $P^{(1)} \leq 0.025$, reject null hypothesis $H^{(1)}$ and proceed to Step 2.

Step 2: In the case of $P^{(2)} > 0.05$, hold null hypothesis $H^{(2)}$. In the case of $P^{(2)} \leq 0.05$, reject null hypothesis $H^{(2)}$.

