HAM-D 21 total score will be analyzed for each visit. Descriptive statistics and two-sided 95% confidence intervals of means will be provided for the observed values and the changes from baseline (each post-dose visit - Baseline) in the HAM-D21 total score at each post-dose visit by treatment group. The point estimates of the mean differences in the changes from baseline between each Lu AA21004 group and the placebo group (each Lu AA21004 treatment group - placebo group) and the two-sided 95% confidence intervals will be provided.

(8) CGI-I score

CGI-I score will be analyzed for each visit. Descriptive statistics and two-sided 95% confidence intervals of means will be provided for the CGI-I score by treatment group. The CGI-I will be performed based on a mixed model for repeated measurements (MMRM) analysis of covariance with CGI-I score at each post-dose visit (Week 1 to Week 8) as a dependent variable, and visit, treatment group, visit-by-treatment group interaction, baseline CGI-S score-by-visit interaction as fixed effects. Least Square (LS) means and the two-sided 95% confidence intervals at each visit will be provided for each treatment group. The point estimates of the differences in the LS means between each Lu AA21004 group and the placebo group (each Lu AA21004 - placebo group) and the two-sided 95% confidence intervals will be provided. The CGI-I score at each post-dose visit (dependent variable) will be analyzed using an ANCOVA model with treatment as a fixed effect and the baseline CGI-S score as a covariate. Least Square (LS) means and the two-sided 95% confidence intervals will be provided for each treatment group. The point estimates of the differences in the LS means between each Lu AA21004 group and the placebo group (each Lu AA21004 group - placebo group) and the two-sided 95% confidence intervals will be provided. The differences in the LS means will be tested for treatment differences.

(9) CGI-S score

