DSST score will be analyzed for each visit. Descriptive statistics and two-sided 95% confidence intervals of means will be provided for the observed values and the change from baseline (each post-dose visit - Baseline) in the DSST score at each post-dose visit by treatment group. The change from baseline in the DSST score will be performed based on a mixed model for repeated measurements (MMRM) analysis of covariance with change from baseline (post-dose visit - Baseline) in the DSST score at each post-dose visit (Week 1 to Week 8) as a dependent variable, and visit, treatment group, visit-by-treatment group interaction, baseline DSST score-by-visit interaction as fixed effects. Least Square (LS) means and the two-sided 95% confidence intervals at each visit will be provided for each treatment group. The point estimates of the differences in the LS means between each Lu AA21004 group and the placebo group (each Lu AA21004 - placebo group) and the two-sided 95% confidence intervals will be provided. The change from baseline in the DSST score at each post-dose visit (dependent variable) will be analyzed using an ANCOVA model with treatment as a fixed effect and the baseline DSST score as a covariate. Least Square (LS) means and the two-sided 95% confidence intervals will be provided for each treatment group. The point estimates of the differences in the LS means between each Lu AA21004 group and the placebo group (each Lu AA21004 group - placebo group) and the two-sided 95% confidence intervals will be provided. The differences in the LS means will be tested for treatment differences.

(13) PDQ-5 score

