PDQ-5 score will be analyzed for each visit. Descriptive statistics and two-sided 95% confidence intervals of means will be provided for the observed values and the change from baseline (each post-dose visit - Baseline) in the PDQ-5 score at each post-dose visit by treatment group. The change from baseline in the PDQ-5 score will be performed based on a mixed model for repeated measurements (MMRM) analysis of covariance with change from baseline (post-dose visit - Baseline) in PDQ-5 score at each post-dose visit (Week 1 to Week 8) as a dependent variable, and visit, treatment group, visit-by-treatment group interaction, baseline PDQ-5 score-by-visit interaction as fixed effects. Least Square (LS) means and the two-sided 95% confidence intervals at each visit will be provided for each treatment group. The point estimates of the differences in the LS means between each Lu AA21004 group and the placebo group (each Lu AA21004 – placebo group) and the two-sided 95% confidence intervals will be provided. The change from baseline in the PDQ-5 score at each post-dose visit (dependent variable) will be analyzed using an ANCOVA model with treatment as a fixed effect and the baseline PDQ-5 score as a covariate. Least Square (LS) means and the two-sided 95% confidence intervals will be provided for each treatment group. The point estimates of the differences in the LS means between each Lu AA21004 group and the placebo group (each Lu AA21004 group – placebo group) and the two-sided 95% confidence intervals will be provided. The differences in the LS means will be tested for treatment differences.

(14) PDQ-5 single item

PDQ-5 single item will be analyzed for each visit. Descriptive statistics and two-sided 95% confidence intervals of means will be provided for the observed values and the changes from baseline (each post-dose visit - Baseline) in the PDQ single item at each post-dose visit by treatment group. The point estimates of the mean differences in the changes from baseline between each Lu AA21004 group and the placebo group (each Lu AA21004 treatment group - placebo group) and the two-sided 95% confidence intervals will be provided.

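### The supportive DSST and PDQ-5 MMRMs count early-termination scores from Study Day 11 as Week 8 outcomes, which makes them a weak check on the LOCF results

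*SAP*

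**What the plan says.** The SAP's Definition of TIME WINDOW gives DSST and PDQ-5 two post-baseline visits: Week 1 (Study Days 2–10) and Week 8, whose row reads "Week 8 Study Day: 56 $11 \leq$ < 8", that is, Day 11 onward with Follow-up Day below 8. The MADRS/CGI-S and CGI-I tables both have "Week 8 Study Day: 56 50 <= <8" instead. On follow-up days the SAP says: "The day after the last dose of the double-blind study drug will be defined as Follow-up Day 1". A score up to seven days after the last dose therefore qualifies. Within a window the score nearest the scheduled day is taken, so a lone early score is used however far it lies from Day 56.

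SAP section 2.3 (12) models "change from baseline (post-dose visit - Baseline) in the DSST score at each post-dose visit (Week 1 to Week 8) as a dependent variable", and section 2.3 (13) does the same for PDQ-5: "in PDQ-5 score at each post-dose visit (Week 1 to Week 8) as a dependent variable". The CGI scales get the same type of model in section 2.3 (8) and (9); for CGI-I it is an "analysis of covariance with CGI-I score at each post-dose visit (Week 1 to Week 8) as a dependent variable".

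Protocol section 9.3.5 and Appendix A footnote (c) have the Visit 8 assessments, including DSST and PDQ-5, done at early termination (ET), within seven days of discontinuation where possible.

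**The concern.** An MMRM takes the visit label as the time point. Once a Day 14 score is labelled Week 8, the model treats it as an observed eight-week outcome and not as a missing one. Cognition after eight weeks is a secondary objective (protocol section 5.1.2), and its declared endpoints are LOCF only. A reader would naturally use the MMRM to ask whether the LOCF result depends on carrying early scores forward. As written it cannot answer that well, because it uses most of those same scores as Week 8 data. If ET rates differ between arms, the estimate can also move in either direction.

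**Working it through.** **1. Apply the windows to each Study Day.**

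| Study Day | DSST, PDQ-5 | CGI-I, CGI-S, MADRS |
|---|---|---|
| 2–10 | Week 1 | Week 1 |
| 11–21 | Week 8 | Week 2 |
| 22–35 | Week 8 | Week 4 |
| 36–49 | Week 8 | Week 6 |
| 50 on | Week 8 | Week 8 |

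The labels differ on 49 − 11 + 1 = 39 days. The DSST/PDQ-5 window opens 56 − 11 = 45 days before the scheduled day. The CGI window opens 6 days before it, and the protocol's own visit window is ±3 days. Patients with a true Week 8 score are unaffected, because the nearest-day rule selects it.

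**2. Compare with the SAP's own pattern.** The other bounds are midpoints between scheduled visits:
- MADRS and CGI: (7+14)/2 = 10.5, (14+28)/2 = 21, (28+42)/2 = 35, (42+56)/2 = 49.
- Laboratory, weight and ECG: (28+56)/2 = 42.

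The same rule for Days 7 and 56 gives (7+56)/2 = 31.5, a boundary at Day 31/32. Day 11 instead matches the MADRS Week 1/Week 2 boundary, with every later day assigned to Week 8.

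**3. Overlap with LOCF.** Week 8 (LOCF) opens at Day 2. A discontinuer with an ET score from Day 11 on contributes that same score to both analyses. They part only for patients whose last score falls on Days 2–10, which LOCF carries forward and the MMRM treats as missing at Week 8.

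**4. Size.** The documents give no ET rate and no DSST effect or SD, so every input here is assumed: mean Week 8 change 8 (active) against 6 (placebo), 160 per arm, ET day uniform over Days 2–55 and unrelated to score, all ET visits attended. With p the ET share and m the mean Week 8 change,

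shift = −c × (pA·mA − pP·mP), where c = (39/54) × (mean share of change not yet accrued on Days 11–49).

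- Linear accrual: the mean day is 30, so c = 39/54 × 26/56 = 0.335.
- Early plateau, accrual (1 − e^(−d/14))/(1 − e^(−4)): the mean accrued share is 0.857, so c = 39/54 × 0.143 = 0.104.

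| ET active/placebo | pA·mA − pP·mP | Linear | Plateau |
|---|---|---|---|
| 20%/10% | 1.6 − 0.6 = 1.0 | 1.66 | 1.90 |
| 10%/20% | 0.8 − 1.2 = −0.4 | 2.13 | 2.04 |
| 15%/15% | 1.2 − 0.9 = 0.3 | 1.90 | 1.97 |

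Simulated MMRMs (SD 9, correlation 0.6) gave 1.65, 2.16 and 1.90 under linear accrual, and 1.94, 2.04 and 1.99 under the plateau. They assume an unstructured covariance. The SAP states that ("the same, unstructured covariance matrix is assumed") only for the primary model, not in section 2.3. With balanced ET of 5–15% and linear accrual the shift is 0.335 × p × 2, or 0.03 to 0.10.

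**5. A Day 50 bound, same assumptions, linear accrual.** The simulated estimates are 2.02, 1.99 and 1.98. The standard error rises from 1.02–1.03 to 1.04–1.07. Root mean squared error, as written against Day 50, is 1.083 and 1.049 (20%/10%), 1.038 and 1.060 (10%/20%), and 1.025 and 1.044 (15%/15%).

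If ET depends on the score, the as-written window gives 1.44–2.60 and Day 50 gives 1.80–2.09. Over 12 such scenarios, with and without a true effect, Day 50 was nearer the truth in 9, as written in 1, and 2 tied.

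**The case against.** The case for leaving the plan alone has real weight.

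- **Importance is limited.** Protocol section 6.2.4 describes the use of DSST and PDQ-5 as exploratory, and SAP section 2.4.5 makes everything beyond the primary analysis supportive and unadjusted. This stands, and it sets the priority.
- **The size rests on the time course.** With an early plateau the shift nearly vanishes, and the documents give no DSST time course. This stands.
- **Day 50 is not the same treatment as CGI receives.** In the CGI models a Day 11–49 score stays in as Week 2, 4 or 6. DSST and PDQ-5 have no such visits, so the score leaves the MMRM altogether and Week 8 is predicted from baseline and Week 1. This stands as a cost.
- **Less bias is not always less error.** By root mean squared error the planned window is slightly better in two of the three linear scenarios and in all three plateau ones. This stands, but it does not restore the MMRM as a check on LOCF.
- **Evaluability rules are unseen.** The windows apply to data that are "non-missing and acceptable according to the" Handling Rules for Analysis Data, which are not among the documents. They could already exclude some ET scores, though nothing in the SAP says that they do.
- **Every day must fall somewhere.** With two scheduled visits, some bound has to be chosen. That is true, but the SAP's midpoint pattern would put it near Day 32, so it does not explain Day 11.

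**Conclusion.** The point holds for the DSST and PDQ-5 MMRMs: ET scores from Days 11–49 enter as observed Week 8 outcomes, and the models largely reuse the LOCF data. The effect is on how supportive cognitive results are read. On the assumed inputs the estimate for a true difference of 2.0 is about 1.65 to 2.16 under linear accrual. Under an early plateau it is about 1.94 to 2.04 in simulation (1.90 to 2.04 by the formula). The standard error is near 1.0, and the shift is small when ET is balanced. The reading of the windows is firm; the size is not.

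A reader might infer more than the documents support:
- **That the trial's conclusion is at risk.** The primary MADRS model opens Week 8 at Day 50, and the secondary endpoints are declared as LOCF. Neither changes.
- **That these MMRMs are simply LOCF.** They differ for patients whose last score falls on Days 2–10.
- **That the MMRM is the only analysis able to treat dropouts as missing.** The by-visit ANCOVA in section 2.3 could also do so, given a narrower window.
- **That HAM-D and SDS need the same correction.** Their Week 8 window opens at Day 2, but they have no MMRM.
- **That Day 50 removes all bias.** It does not if ET depends on the score.

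**What to change.** For the DSST and PDQ-5 MMRMs only, open Week 8 at Study Day 50. ET scores on Days 11–49 are then missing at Week 8 in the model and count only in Week 8 (LOCF). If treatment codes are already open, keep the planned table and add the Day 50 version as a labelled sensitivity table. State the covariance structure for these models as well.

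Keep the by-visit ANCOVAs, with a footnote that Week 8 includes ET scores from Day 11 (DSST, PDQ-5) or Day 2 (HAM-D, SDS). A Day 50 ANCOVA would be restricted essentially to completers and is not a clear gain.

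The cost is one window entry and a re-run of two models. With 10–20% ET, uniform over Days 2–55 and all visits attended (assumed), 160 × 0.10 × 39/54 ≈ 12 to 160 × 0.20 × 39/54 ≈ 23 scores per arm leave the MMRM, and its standard error rises by about 2–5%. No score leaves the LOCF tables. If the Handling Rules already exclude some ET scores, both the problem and the cost are smaller.

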9.1.15 ECG Procedure

A standard 12-lead ECG will be recorded. The investigator (or a qualified observer at the study site) will interpret the ECG using 1 of the following categories: within normal limits, abnormal but not clinically significant, or abnormal and clinically significant. The following parameters will be recorded on the eCRF from the subject's ECG trace: RR interval, PR interval, QT interval, QRS interval, and QTcB interval. QTcF interval will be calculated by the sponsor. ECG traces recorded on thermal paper should be photocopied to avoid degradation of trace over time.

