3.3.2 Vital Signs, Physical Findings and Other Observations Related to Safety

3.3.2.1 Vital Signs and Weight

Analysis Set: Safety Analysis Set

Analysis Temperature

Variable(s): Systolic Blood Pressure

Diastolic Blood Pressure

Pulse Rate

Weight

Categories: Results based on PCS [Meet PCS Criteria, Does not meet PCS Criteria]
Criteria

Visit: Temperature, Systolic Blood Pressure, Diastolic Blood Pressure, Pulse Rate:
Screening, Placebo Lead-in, Baseline, Week 1, Week 2, Week 4, Week 6, and
Week 8

Weight: Screening, Placebo Lead-in, Baseline, Week 4, and Week 8

PCS: Entire post-dose period

Analytical The following summaries will be provided for the above analysis variable(s).

Method(s):
(1) Descriptive statistics for observed values at each visit and changes from
baseline at each visit (each post-dose visit [Week 1 to Week 8] - Baseline)
(2) Plots over time for each subject
(3) Frequency distributions of the results based on PCS Criteria during the

entire post-dose period
 Refer to the Appendix of this Statistical Analysis Plan if a vital sign parameter has lower or upper PCS Criteria.

3.3.2.2 12-lead ECG

Analysis Set: Safety Analysis Set
 Analysis RR Interval
 Variable(s): PR Interval
 QT Interval
 QRS Interval
 QTcB Interval
 QTcF Interval
 12-Lead ECG Interpretation [Within Normal Limits, Abnormal but not Clinically Significant, Abnormal and Clinically Significant]
 Categories: Results based on PCS [Meet PCS Criteria, Does not meet PCS Criteria]
 Visit: Screening, Placebo Lead-in, Baseline, Week 4, and Week 8
 PCS: Entire post-dose period
 Analytical For each variable other than 12-lead ECG interpretations, summaries (1) to (3) will be provided by treatment group.
 Method(s): For 12-lead ECG interpretation, summary (4) will be provided by treatment group.
 (1) Descriptive statistics for observed values at each visit and changes from baseline at each visit (each post-dose visit [Week 4, Week 8] - Baseline)
 (2) Plots over time for each subject
 (3) Frequency distributions of the results based on PCS Criteria during the entire post-dose period
 Refer to the Appendix of this Statistical Analysis Plan if a ECG laboratory parameter has lower or upper PCS Criteria.
 (4) Shift tables at baseline and each post-dose visit

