7	Others	
 • QT_CF interval = (QT interval) / ([QT_CB interval]² / [QT interval]²)^{0.33} (rounded off to the whole number) • Among the laboratory test items, the following data will not be included if it is from a postprandial specimen. Glucose, lipids (triglycerides, total cholesterol, HDL cholesterol, LDL cholesterol [Direct method]) 	New addition
13	1.2.1 Summary of Demographics and Other Baseline Characteristics Weight (kg) BMI(kg/m ²)	1.2.1 Summary of Demographics and Other Baseline Characteristics Weight (kg) at Baseline BMI (kg/m ²) at Baseline	To make the time point clear
13	1.2.1 Summary of Demographics and Other Baseline Characteristics Pharmacotherapy for Current Episode	1.2.1 Summary of Demographics and Other Baseline Characteristics (Deleted)	Because it was not an item to be collected in the CRF
15	1.2.1 Summary of Demographics and Other Baseline Characteristics Frequency distributions for categorical variables and descriptive statistics for continuous variables will be provided by treatment group and overall.	1.2.1 Summary of Demographics and Other Baseline Characteristics The following summaries will be provided for the above analysis variable(s). When the randomized set is analyzed, the frequency distribution will be provided for each	To make the subjects for distributions clear

Page	Before Change	After Change	Reason for Change
		treatment group and overall. However, weight, BMI, and efficacy endpoints (MADRS total score, HAM-D17 total score, CGI-I score, CGI-S score, SDS total score, DSST score, and PDQ-5 score) will target only the randomized set.	
16	1.2.3 Medication History and Concomitant Medications preferred medication names	1.2.3 Medication History and Concomitant Medications generic names	Due to error in writing

Page	Before Change	After Change	Reason for Change

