	SI	mmol/L	Measured value is \leq 125 or \geq 155
Calcium	CV	mg/dL	Measured value is \leq 0.8-fold of LLN or \geq 1.2-fold of ULN
	SI	mmol/L	Measured value is \leq 0.8-fold of LLN or \geq 1.2-fold of ULN
Triglycerides	CV	mg/dL	Measured value is \geq 1.5-fold of ULN
	SI	mmol/L	Measured value is \geq 1.5-fold of ULN
Total Cholesterol	CV	mg/dL	Measured value is \geq 1.5-fold of ULN
	SI	mmol/L	Measured value is \geq 1.5-fold of ULN
HDL Cholesterol	CV	mg/dL	Measured value is \geq 1.5-fold of ULN
	SI	mmol/L	Measured value is \geq 1.5-fold of ULN
LDL Cholesterol	CV	mg/dL	Measured value is \geq 1.5-fold of ULN
	SI	mmol/L	Measured value is \geq 1.5-fold of ULN

Vital Signs (Blood Pressure, Pulse Rate) and Weight

Analysis Variable(s):	Unit	Definition of PCS
Pulse Rate	bpm	Measured value is ≤ 50 and change* is ≤ -15 or measured value is ≥ 120 and change* is ≥ 15
Diastolic Blood Pressure	mmHg	Measured value is ≤ 50 and change* is ≤ -15 or measured value is ≥ 105 and change* is ≥ 15
Systolic Blood Pressure	mmHg	Measured value is ≤ 90 and change* is ≤ -20 or measured value is ≥ 180 and change* is ≥ 20
Weight	kg	Change rate* is $\leq -7\%$ or $\geq 7\%$

*: Change or change rate from baseline

Resting 12-lead ECG

Analysis Variable(s):	Unit	Definition of PCS
PR Interval	msec	Measured value is < 120 or ≥ 250
QRS Interval	msec	Measured value is < 40 or > 150
QT Interval	msec	Measured value is < 280 or > 500
QTcF Interval	msec	Measured value is < 340 and change* is < -60 or measured value is > 500 and change* is > 60
QTcB Interval	msec	Measured value is < 340 and change* is < -60 or measured value is > 500 and change* is > 60
RR Interval	msec	Measured value is < 500 and change* is ≤ -200 or measured value is > 1200 and change* is ≥ 200

*: Change from baseline

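### The SAP's QTcF formula has its ratio upside down, so it corrects QT in the opposite direction to QTcB

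*SAP*

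**What the plan says.** Protocol section 9.1.15 has the site record "RR interval, PR interval, QT interval, QRS interval, and QTcB interval" on the eCRF and adds that "QTcF interval will be calculated by the sponsor". The derivation is therefore left to the SAP.

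The SAP gives it once as a rule, in the Others list that follows the time-window tables: "QT \text{ interval}) / ([QT_{CB} \text{ interval}]^2 / [QT \text{ interval}]^2)^{0.33" (the quote omits the opening bracket and closing brace), rounded to a whole number. The Appendix 1 change table repeats it for page 7, as an item new in Version 2, with the ratio the same way up: "QT interval) / ([QT_CB interval]² / [QT interval]²)^{0.33". Neither document offers another QTcF formula.

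QTcF then enters SAP section 3.3.2.2: "For each variable other than 12-lead ECG interpretations, summaries (1) to (3) will be provided by treatment group". Those summaries are observed values and changes from baseline, subject plots, and PCS frequencies. Appendix 2 gives QTcF and QTcB the same PCS rule: "Measured value is < 340 and change* is < -60 or measured value is > 500 and change* is > 60".

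**The concern.** QTcB and QTcF are two heart-rate corrections of the same QT, so they should move it the same way and differ only in how far. The printed formula moves it the other way. Giving both intervals identical PCS limits makes sense only if they lie on comparable scales.

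At stake is one reported safety parameter. If the formula is coded as printed, QTcF means and changes from baseline mix the QT signal with heart rate in the wrong direction. The QTcF and QTcB tables would disagree with no visible reason, and PCS flags could be raised falsely or missed.

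**Working it through.** **Step 1: algebra, with no outside definition.**

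QT / (QTcB²/QT²)^0.33 = QT × (QT²/QTcB²)^0.33 = QT × (QT/QTcB)^0.66.

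If QTcB > QT, the factor is below 1 and QTcF < QT. If QTcB < QT, QTcF > QT. Example: QT 371 and QTcB 415 give (415/371)² = 1.251, then 1.251^0.33 = 1.077, then 371/1.077 = 345. On a grid of QT 280 to 520 and RR 450 to 1490 msec, no case with RR other than 1000 put the two corrected values on the same side of QT.

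**Step 2: size of the error.** This needs definitions that the documents do not state. Assume QTcB = QT/RR^(1/2) and QTcF = QT/RR^(1/3), with RR = 60/HR in seconds. Then QTcB²/QT² = 1/RR, and the printed rule is QT × RR^0.33 in place of QT/RR^0.33. The ratio needed is QT²/QTcB² = RR.

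For a true QTcF of 400 msec, with QT = 400 × RR^(1/3):

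| HR | As printed | Ratio swapped |
|---|---|---|
| 50 | 451 | 400 |
| 60 | 400 | 400 |
| 75 | 345 | 400 |
| 90 | 306 | 399 to 400 |
| 100 | 285 | 399 |

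Swapping the ratio is the whole repair. Using 0.33 for 1/3 costs less than 1 msec at HR 90.

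**Step 3: changes from baseline.** With QT unchanged at 380 and HR going from 75 to 85, the printed rule gives 353 to 339 (−14) and the swapped rule 409 to 426 (+17): the sign reverses. At constant HR 75, QT 380 to 400 gives +19 in place of +22.

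**Step 4: PCS flags under Appendix 2.** The ECG values are illustrative, because the documents contain no ECG data.

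1. True QTcF 440 to 505 at HR 75. Printed rule: 379 to 436 (+57), no flag. QTcB: 457 to 524 (+67), flagged.
2. True QTcF constant at 420, HR 65 to 90. Printed rule: 398 to 321 (−77), a false low flag. QTcB: 426 to 449 (+23), none.
3. True QTcF 430 at HR 90 to 505 at HR 70 (+75), a true high event. Printed rule: 329 to 456, no flag. QTcB: 460 to 518 (+58), just short of the required change. QT: 376 to 480, inside its limit ("Measured value is < 280 or > 500"). RR: 667 to 857, none. Every interval criterion misses it.
4. HR 60 with QT 420 to HR 45 with QT 470. Printed rule: 420 to 517 (+97), a false high flag. Swapped rule: 420 to 427 (+7), none.

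**Step 5: how often, under assumed inputs.** Take true QTcF with mean 405, between-subject SD 18 and change SD 12, and HR with mean 70, SD 10 and change SD 8. The printed rule then shows a mean near 372 and an SD of change near 31, against 405 and 12. PCS flags differ for 1.4% to about 2% of draws, depending on how the heart rates are generated. Varying HR mean (65 to 75), HR change SD (7 to 10) and mean HR shift (0 to 5) gives 0.6% to 7.0%. Nearly all of these are false flags. True PCS events are so rare under these inputs that hardly any could be missed.

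**The case against.** The strongest reply is about consequence. QTcF is one of six ECG intervals, all summarised descriptively. It enters no hypothesis test, eligibility rule or discontinuation rule. Investigators do not record it, so no subject would be managed on the wrong number. QT, QTcB, RR and the investigator's ECG interpretation are unaffected, and at a constant heart rate above 60 the QTcB criterion still catches a true high-QTcF event. Protocol section 4.1.2 reports no QT/QTc prolongation potential at doses up to 40 mg/day in healthy adults, so the likelier harm is spurious flags and a contradictory table, not hidden events. All of that stands. It limits the damage but does not make the formula right. Case 3 shows that the QTcB backstop is incomplete when heart rate falls, although it needs a 75 msec rise together with a drop of 20 beats per minute.

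Two further points are fair. The millisecond errors rest on definitions that the documents do not state; the opposite-direction result does not. And a minus sign lost from the exponent would also produce this text. The same orientation in two differently typeset places makes that unlikely, and a look at the original page settles it.

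Finally, the harm depends on what was coded, which the documents do not show. If the program is right, it departs from the SAP without a record, so the text needs correcting in either case.

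**Conclusion.** The concern holds. The SAP's sole definition of QTcF has its ratio inverted, and by algebra alone it corrects QT in the opposite direction to QTcB. Under the usual definitions its values are right only at HR 60: for a true value of 400 they are 55 msec too low at HR 75 and 51 msec too high at HR 50. Changes from baseline are generally wrong and can reverse sign. PCS flags can err in both directions, although most would not change. The frequency figures rest on assumed ECG distributions and are illustrative. The effect is confined to the QTcF outputs in SAP section 3.3.2.2. It should be corrected because it is a definite error in a reported safety variable and costs almost nothing to repair.

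**What to change.** - In the SAP's Others list, print QTcF = QT / ([QT]² / [QTcB]²)^0.33.
- Record the correction as a new row in the Appendix 1 change table of a new SAP version, leaving the existing Version 2 row as history.
- QT / (RR/1000)^0.33 is an alternative, since RR is on the eCRF and Appendix 2 gives it in msec. The two may differ slightly, because RR and QTcB are recorded separately, so name one.
- Check which form the analysis program uses. Rerun the QTcF summaries, changes, plots and PCS tables only if the printed form was coded.

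The cost is one line of SAP text, one change-table row and a check of one derivation line. No new data are needed.
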